Our clinic-based studies yielded key findings related to biomarkers, Sound Sweeps performance, and predictors of therapeutic sensitivity to a full course of TCT. **First**, baseline levels of EAIP predicted TCT learning during 1h of Sound Sweeps. **Second**, SZ patients exhibited clinical, neurocognitive and functional gains after 30h of TCT, and changes in EAIP during the first hour of Sound Sweeps testing predicted neurocognitive and clinical gains after a full 30h course of TCT. In total, these findings with memantine, EAIP, TCT learning, and clinical outcomes provide a strong empirical and conceptual framework for a mechanistically-based hypothesis to be tested via the proposed randomized, placebo-controlled 30h pilot trial of (memantine+TCT) vs. (placebo+TCT). Via the below Aims, this application provides efficient pilot testing of this PACT strategy in antipsychotic-medicated SZ patients, using Go/No-Go criteria to inform a future, fully-powered “Confirmatory Efficacy trial”:

AIM 1 – Replicate previous findings of memantine target engagement on TCT learning: In two, 1h tests, determine if memantine increases Sound Sweeps TCT learning in SZ patients (n=54) vs. placebo.

AIM 2 – Test clinical, neurocognitive and functional impact of memantine on TCT, and its relationship to target engagement: In a 30-session course of TCT over 10 weeks, determine if memantine augments the magnitude, rate and/or durability of TCT-induced gains, and whether these gains are associated with target engagement.

AIM 3 – Explore biomarkers of memantine-induced gains: Determine whether higher basal levels of EAIP (and related functional and neurophysiological measures) or changes in these measures across the first hour of Sound Sweeps predict greater sensitivity to memantine-enhanced clinical, neurocognitive or functional gains among SZ patients receiving combined memantine+TCT.

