C. Approach: This application uses an **experimental therapeutics approach** in an "efficient pilot test" of the hypothesis that MEM will augment TCT-induced learning, and thereby clinical, neurocognitive and functional gains, in antipsychotic-medicated SZ patients. In so doing, this application will advance a PACT model for TCT in two specific ways: 1) building on strong preliminary findings, this application will confirm target engagement and identify biomarkers that predict the effectiveness of MEM-enhanced TCT learning, and 2) this application will provide the first randomized controlled trial to assess the ability of medication-enhanced TCT learning (target engagement) to produce significant and lasting clinical, neurocognitive and functional gains in biomarker-characterized SZ patients. In this way, **this application responds to RFA-MH-18-705**, "Development of Psychosocial Therapeutic and Preventive Interventions for Mental Disorders", which supports *"efficient pilot testing of novel psychosocial therapeutic and preventive interventions for mental disorders... using an experimental therapeutics approach."* Moreover, in this application, *"results, whether positive or negative, will provide information of high scientific utility and... support 'go/no-go' decisions about further development or testing of the intervention."* The application uses a *"novel intervention strategy"* - the PACT model - in a design that will *"replicate target engagement and relate change in the... target/mechanism to clinical benefit."* Findings from this pilot study will **inform a future, fully-powered Confirmatory Efficacy trial**.

This application will confirm target engagement by demonstrating that MEM (20 mg po) enhances APS learning in a Sound Sweeps session in biomarker-characterized AP-medicated SZ patients; these patients will then be randomized to a 30-session RCT of TCT+MEM (n=27) vs. TCT+PBO (n=27). Findings will determine whether MEM augments the known neurocognitive and clinical benefits of TCT, and whether APS "MEM sensitivity" - based on APS gains in 2 test sessions - predicts the therapeutic impact of MEM over a 30-session TCT regimen. Other predictive biomarkers will be explored, including baseline neurocognitive (MCCB scores), ERP (MMN, P3a) / EEG (ASSR, evoked theta band power) measures, and MEM effects on auditory discrimination and on ERP changes across the first Sound Sweeps sessions.

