Staff assessing outcome measures are blind to treatment arm, and for some measures receive training using videotaped and practice interviews until achieving high (ICC>.80) reliability based on 20 assessments by 2 raters. We achieve high inter-rater reliability (e.g., ICC>0.85 for PANSS total), and check for rater drift each 90d.

Specific Procedures: TCT is completed with a dedicated room and equipment. Staff trained with a UCSD-developed “TCT Clinician Competence Assessment” monitor TCT, clarify instructions and provide encouragement as needed. **In the initial “biomarker testing” session (Test 1),** subjects complete 1-h of Sound Sweeps to generate a “Pre-Training APS score” as described previously (Fig. 3) under identical circumstances and timelines as for the Test 2 session described below. Treatment group assignment (PBO vs. MEM) is then made using stratified random sampling (above) and 5-7 days later patients ingest either PBO (n=27) or 20 mg MEM (n=27) 240 min before completing the Sound Sweeps session (“Test 2”). MEM effects on APS learning are assessed both within-subject (APS (Test 1 - Test 2) for MEM group subjects: a key measure of **MEM sensitivity**) and between subjects (APS Test 2, PBO vs. MEM groups). After Test 2, all subjects are prescribed daily PBO or MEM using a standard titration schedule (MEM 5 mg at hs→ 5 mg bid→ 5 mg am/10 mg hs→ 10 mg bid over 3 weeks). Participants return to the laboratory to complete 1h TCT per our established procedures^{2,34}, which includes 5 modules of auditory/verbal processing exercises. Each module increases in difficulty as performance improves: **1) Sound Sweeps; 2) Syllable Identification:** Patients distinguish between 2 similar phonemes (e.g., “ba” vs. “da”), differing only in their voice onset time; **3) Word Matching:** Subjects match short similar-sounding consonant-vowel-consonant words (e.g., bad, dad); **4) Listen & Do:** Subjects reconstruct a spoken series of instructions and use a computer mouse to click icons on the screen in a specified order. This exercise is designed to stimulate verbal WM processes supported by the lateral PFC as well as premotor and motor processes. **5)**

Table 1. “Go” criteria: #1, plus at least one of #'s 2, 3 & 4 ($d>0.5$)

1. **Target engagement:** APS learning, MEM > PBO, p<0.05
2. **Greater** clinical, neurocognitive **or** functional gains:
 - ↓PANSSt, ↑MCCB-C **or** ↑Fnxn: MEM+TCT > PBO+TCT
3. **Faster** clinical, neurocognitive **or** functional gains:

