Biomarkers from Tests 1-2 will be assessed as predictors of target engagement (Aim 1) and PACT sensitivity (Aim 2); in some cases, these measures will also inform mechanistic models for PACT: 1. **MEM-enhanced APS learning is both an outcome measure** (Aim 1, “target engagement”) and **candidate predictor** of clinical outcome (Aim 2); 2. Baseline and MEM-enhanced **MCCB A/V scores** are associated with APS MEM sensitivity⁷³, and thus may predict clinical outcome (Aim 2); 3. **EEG** measures of early auditory information processing variably predict response to early APS learning⁸⁷, MEM-enhanced APS learning⁷⁴, and TCT outcomes³¹. EEG/ERPs are acquired via 64-channel recording systems and assessed in the same order, as per^{49,107}: MMN/P3a/Theta power/Phase locking (25 min; Oddball Paradigm), ASSR (6 min). 4. **Auditory discrimination**: Words-In-Noise (WIN; NIH Toolbox) and Speech-In-Noise (Quick-SIN; Etymotic Research) are acquired at Tests 1-2, TCT hour 30 and week 22. Both measures assess the ability to recognize speech over background noise, mimicking a conversation in a noisy environment, and are thought to index peripheral (WIN) vs. more central (QuickSIN) auditory processing. MEM-enhanced APS learning may predict PACT outcome (Aim 2); gains in auditory discrimination over 30 hours of TCT, and their augmentation by MEM, will be tracked to inform evolving models of PACT mechanisms. **Predictions:** First and foremost, **target engagement (MEM-enhanced APS learning) will predict MEM-enhanced TCT outcomes (Aim 2) as described below**. Exploratory analyses will test **secondary** predictions: for example, high vs. low baseline P3a amplitude and faster P3a latency will predict greater target engagement (Aim 1), and greater MEM-enhanced TCT outcome (Aim 2). MEM-enhanced (Test 2 vs. 1) ERPs, auditory discrimination and neurocognitive (A/V) measures will also be explored as outcome (Aim 2) predictors; significant pre- vs. post-TCT changes in ERP source dynamics will also be examined for mechanistic characterization⁷¹. Robust biomarker predictors will be examined as moderators of both indirect and direct paths between treatment and outcome in a future Confirmatory Efficacy trial.

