Aim 1 – Confirm target engagement: The primary dependent measure of target engagement is MEM-enhanced APS learning. APS learning is defined as the reduction in Sound Sweeps APS threshold (ms) Test 1 to Test 2 assessment. Target engagement was demonstrated in Fig. 3⁷⁶, and will be confirmed if APS learning is increased by MEM (note that MEM and PBO groups are matched by Test 1 PBO performance via stratified randomized assignment). As appropriate, effect sizes and inferential statistics are based on standard regression or LME models with random intercepts. A significant interaction between contrast coded drug (PBO vs. MEM) and Test (Test 1 vs. Test 2) predictors on APS learning is a “Go” criteria and confirms target engagement.

Aim 2 – Test clinical, neurocognitive and functional impact of MEM on TCT, and its relationship to target engagement: We will determine if MEM+TCT produces greater, faster or more durable clinical, neurocognitive or functional gains from baseline, compared to PBO+TCT, over a 30-session course of TCT. A Cohen’s $d > 0.5$ for the main effect of drug (PBO vs. MEM) or drug x session (#10, 20, 30) interaction in an LME model is the primary “Go” criteria. The effect of drug assesses “greater” gains. Reverse Helmert contrasts for session assesses “faster” gains. A separate model comparing differences in outcomes at 12-weeks post-TCT assesses “more durable” gains. Secondary analyses will examine whether change in MEM-enhanced APS learning (“within-subject” target engagement; Aim 1) predicts gains in Aim 2 outcome measures.

Aim 3 – Biomarkers of MEM-induced gains: We will determine if baseline levels of specific neurocognitive or EEG-based measures, or changes in specific measures with initial MEM exposure (Test 2 vs. 1), predict greater sensitivity to MEM-enhanced neurocognitive, clinical or functional gains over 30-h of TCT. Regression analyses will assess whether specific candidate biomarkers predict MEM-enhanced gains in outcome measures.

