4.2. Study Design

4.2.a. Narrative Study Description

Screened, eligible patients complete clinical, neurocognitive and functional measures and candidate biomarkers (EEG, QuickSIN, WIN). Aim 1 is completed in 2 tests, approximately 1 week apart. In Test 1, Sound Sweeps are tested after PBO for all subjects, who are then randomized to TCT+PBO vs. TCT+MEM arms (n=27/arm) using stratified random sampling (over sex, age and high/low Test 1 APS learning) blind to arm identity, similar to our previous studies. Test 2 follows approximately 5-7 d later; this test is identical to Test 1, except that subjects receive their assigned study drug (PBO vs. MEM (20 mg po) 1 hour prior to Sound Sweeps. Tests 1 and 2 are used to assess target engagement (Aim 1: MEM-enhanced APS learning) and MEM effects on auditory discrimination (QuickSIN, WIN). Our design allows for 20% attrition from enrollment (n=69) to completion of target engagement testing (n=54). For Aim 2, TCT in these same subjects is scheduled 3 d/week (M-W-F) for 1-h/d, recognizing the need for flexibility (T-Th are "make-up days"), and continues until a subject completes 30-h (approximately 10-12 weeks). TCT is delivered by trained staff. 60 min prior to each TCT session, patients take either PBO or 20 mg MEM, as per arm assignment. Patients and staff are blind to study arm; staff are blind to patients' baseline or post-intervention assessments. Outcome metrics assess symptom, neurocognitive and functional changes after 10, 20 and 30 TCT sessions, and 12 weeks post-TCT. Candidate biomarkers are re-tested after completion of 30 sessions of TCT.

4.2.b. Primary Purpose

Treatment

4.2.c. Interventions

Type	Name	Description
Behavioral (e.g., Psychotherapy, Lifestyle Counseling)	Targeted Cognitive Training (TCT)	Thirty, one-hour sessions over approximately 10 weeks, of computerized cognitive training modules.
Drug (including placebo)	memantine	The pro-cognitive medication, memantine (placebo vs. 20 mg) will be administered orally, 1 hour prior to targeted cognitive training, in a double-blind, randomized design.

4.2.d. Study Phase

Phase 2/3

Is this an NIH-defined Phase III Clinical Trial?

Yes No

4.2.e. Intervention Model

Parallel

4.2.f. Masking

Yes No

Participant Care Provider Investigator Outcomes Assessor

4.2.g. Allocation

Randomized

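### The memantine-arm change from Test 1 to Test 2 is not individual drug response, so its correlation with TCT benefit cannot be read as memantine-specific without the placebo arm

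*Combined protocol and SAP*

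**What the plan says.** Research Strategy, Specific Procedures: "MEM effects on APS learning are assessed both within-subject (APS (Test 1 - Test 2) for MEM group subjects: a key measure of" memantine sensitivity. The same sentence adds a between-arm comparison at Test 2, but the sensitivity score itself is defined for memantine-arm patients only.

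The order of conditions is fixed. Synopsis 4.2.a: "In Test 1, Sound Sweeps are tested after PBO for all subjects, who are then randomized to TCT+PBO vs. TCT+MEM arms". Of Test 2, some 5-7 days later, it says "this test is identical to Test 1, except that subjects receive their assigned study drug". Memantine patients therefore supply a placebo-memantine pair, and placebo patients a placebo-placebo pair.

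The score is then used as a predictor:

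- Approach: the study will determine whether it "predicts the therapeutic impact of MEM over a 30-session TCT regimen".
- Biomarkers: the leading prediction is that "target engagement (MEM-enhanced APS learning) will predict MEM-enhanced TCT outcomes (Aim 2) as described below".
- Data Analysis, Aim 2: "Secondary analyses will examine whether change in MEM-enhanced APS learning", identified there as the within-subject Aim 1 measure, predicts Aim 2 gains.
- Biomarkers, for the other candidates: "MEM-enhanced (Test 2 vs. 1) ERPs, auditory discrimination and neurocognitive (A/V) measures will also be explored as outcome (Aim 2) predictors".
- Specific Aims, Aim 3: the question concerns "gains among SZ patients receiving combined memantine+TCT".
- Item 11 of the question-and-answer part (negative results): the score could still serve as a predictive biomarker if the arms do not differ on average.

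No section gives the placebo arm's change a role in these linking analyses, states a predictor-by-arm term, or adjusts for Test 1.

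**The concern.** A single patient's placebo-to-memantine change cannot be split into drug response and everything else that differs between two sessions a week apart. If the non-drug part is itself related to later benefit, a correlation found in the memantine arm alone would appear just as well in patients who never took memantine. The placebo-placebo pairs would show this, but the analysis as written does not use them.

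The plan's own background makes this plausible. In the earlier TCT trial, which gave no memantine, P3a change over the first Sound Sweeps hour correlated 0.58 with verbal-learning gain and -0.54 with hallucinations (Predictors of gains from 30-h of TCT). That is an EEG change within one session, not an APS change between tests, but it shows that early drug-free change can predict TCT benefit.

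At stake is the mechanistic claim that links target to benefit, and the choice of a marker for the next trial. The Outcome and Go Decisions section says that a meaningful predictor would count in favour of a Go.

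**Working it through.** **Inputs from the plan.** Mean effect 0.5 SD, 80% power, two-sided alpha 0.05, retest correlation r = 0.8, 27 per group (Power analyses; 4.4); 18 expected completers per arm (Subject throughput).

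**Assumed, because the documents give no value.** The between-patient SD of true drug response, tau (0.25, 0.5, 1.0 SD), and the correlation of non-drug change with benefit (0.2 to 0.5).

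**1. The plan's sample size.** Treat Aim 1 as a two-arm comparison of change.
- SD of change = sqrt(2(1 - 0.8)) = 0.632.
- n per arm = 2 x (0.632 x (1.960 + 0.842)/0.5)^2 = 25.1, so 26. The t-based version gives 26.1, so 27, which is the stated figure.
- Power at 27 is 81.3% (t).

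The plan's sample size is therefore consistent with a non-drug SD of change of 0.63.

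**2. Non-drug variation in one patient's change.** Variance 2(1 - 0.8) = 0.40, SD 0.63, against a planned mean effect of 0.5. At r = 0.5 the SD would be 1.0.

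**3. Tie to Test 1.** In learning units, with no drug variation, corr(Test 2 - Test 1, Test 1) = -sqrt((1 - r)/2) = -sqrt(0.1) = -0.32. It is -0.50 at r = 0.5.

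**4. Reliability as a measure of drug response.** tau^2/(tau^2 + 0.40):

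| tau | reliability | observed r if true r = 0.5 | power, n = 27 | power, n = 18 |
|---|---|---|---|---|
| 0.25 | 0.14 | 0.18 | 15% | 11% |
| 0.5 | 0.38 | 0.31 | 35% | 24% |
| 1.0 | 0.71 | 0.42 | 60% | 42% |

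Observed r = 0.5 x sqrt(reliability); power is by Fisher z for the memantine-arm correlation. The smallest correlation detectable with 80% power is tanh(2.80/sqrt(n - 3)): 0.52 at n = 27 and 0.62 at n = 18.

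**5. False attribution to the drug.** Simulation, 4,000 trials per cell, r = 0.8, tau = 0, non-drug change correlated with benefit as shown:

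| correlation | memantine arm only, n = 27 | memantine arm only, n = 18 | change-by-arm test |
|---|---|---|---|
| 0.2 | 16% | 13% | 4% |
| 0.3 | 33% | 23% | 6% |
| 0.4 | 56% | 38% | 5% |
| 0.5 | 78% | 59% | 5% |

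A separate simulation of the same scenario gave 21-31% at 0.3 and 54-76% at 0.5. Over 0.3 to 0.5, roughly 20 to 75% is a fair summary.

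**6. What using both arms can detect.** With a true link of 0.5 and tau 0.25 / 0.5 / 1.0, the change-by-arm test has power 10% / 16% / 19% at 27 per arm and 8% / 12% / 13% at 18. Adjusting for Test 1 adds little. At tau = 0.3 the drug-response share is 0.09/(0.09 + 0.40) = 18% for the raw change and 0.09/(0.09 + 1 - 0.64) = 20% after adjustment.

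**The case against.** **The stakes are bounded.** The linking analysis is labelled secondary, and Table 1 does not require it for a Go. A reader might infer that the target-engagement test shares the fault. It does not: the Aim 1 criterion is a drug-by-Test interaction in randomised arms, which removes average practice and average regression to the mean. This stands.

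**Common practice does not matter.** A gain shared by all patients moves the mean and leaves a correlation unchanged, and Fig. 3 reports no carry-forward after placebo. This stands for the average. Retest error and individual differences in practice remain.

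**The model may be under-specified and not wrong.** The Neurocognition section mentions moderators, 4.4 speaks of gains from adding memantine, and formal moderated mediation is deferred to a larger trial. But the one definition given restricts the score to the memantine arm, and no section brings in the placebo pairs.

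**Some tempting readings go too far.**
- That the score is mostly noise: reliability runs from 0.14 to 0.71 over the assumed tau, and at -0.32 Test 1 explains only 10% of the change.
- That a positive link would just show slow starters gaining more: the plan expects higher baseline auditory processing to predict larger gains, so the direction of any distortion is unknown.
- That the earlier APS study escaped the fault as a balanced crossover: that label belongs to the EEG studies in Fig. 2, Fig. 3 says only within-subject, and an individual crossover difference carries the same retest error.

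**A slope difference tests moderation, not whether the target matters.** Item 6 hypothesises that learning itself drives benefit. If it does so equally in both arms, the slopes are equal. Simulated with assumed values (r = 0.8, tau = 0.3, link 0.5), a steeper memantine slope is significant in about 5% of trials and a common slope in 86-96%. This stands, and it shapes the fix.

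**Conclusion.** The concern holds for the individual-level score and for what may be concluded from it. A memantine-arm correlation between this change and Aim 2 gain is not evidence of a drug-specific link. The risk is greatest in the case item 11 allows, where the score is kept as a predictor although the arms do not differ.

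The 0.63 SD and the tie of about -0.3 to Test 1 follow from the plan's r = 0.8. The plan does not say whether that value is for APS level or APS learning. Learning is itself a difference of two scores, so its retest correlation may be lower and both figures larger. The false-attribution rates depend on the assumed correlation between non-drug change and benefit; if it is zero, the memantine-arm test keeps its nominal 5%.

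A reader might conclude that the score cannot carry any target-to-benefit analysis. The documents do not support that: the placebo-placebo pairs are already planned, and with them the question can be put validly, though weakly.

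**What to change.** In Specific Procedures, Biomarkers and Data Analysis (Aims 1 to 3):

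1. Fix one definition of APS learning. Measuring Target Engagement uses pre minus post within a session, Aim 1 uses the threshold reduction from Test 1 to Test 2, and Specific Procedures writes a Test 1 minus Test 2 difference in APS. Scale and sign must be settled.
2. Compute the Test 1-to-Test 2 measure in both arms.
3. Model each Aim 2 gain on Test 2 learning, adjusted for Test 1 learning, with arm and the learning-by-arm interaction. Report the slope and interval in each arm.
4. State the reading in advance. A common slope supports a relation between learning and TCT benefit. Only a slope difference, steeper under memantine, supports a memantine-specific sensitivity marker.
5. Do not call the memantine-arm change drug response, or a predictor of memantine benefit, on the memantine-arm correlation alone.
6. Treat the EEG, WIN/QuickSIN and attention/vigilance change scores in the same way.

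**Cost.** Analysis wording only, with no new data or visits. The interaction test has about 8 to 19% power at 18 to 27 per arm (simulated for the unadjusted change-by-arm form), so it must be labelled exploratory. The change restores correct interpretation, not power.

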Outcome and “Go Decisions”. In addition to confirming “target engagement”, this application tests the hypothesis that SZ patients given MEM +TCT will exhibit greater, faster and/or more durable improvements (change from baseline) in symptoms, neurocognition and/or function compared to patients given PBO+TCT, and that this enhanced clinical response will be associated with greater MEM-enhanced TCT learning.

The small “n” necessitated by the 3-year timeline and demanding treatment schedule greatly constrains the total number of outcome measures.

Moreover, the plan to assess not only magnitude but also rate and durability of PACT gains triples the number of primary analyses. Thus, we selected only one **primary** clinical, neurocognitive and functional outcome measure (Table 1) – recognizing that they are relatively “blunt” metrics - but will track several other, more focused, measures as well as inter-measure correlations in exploratory analyses to inform future studies.

A “Go” decision requires: 1) confirmation of target engagement (APS learning, MEM>PBO, p<0.05); 2) evidence of gains from PACT ($d \geq 0.5$ (MEM > PBO)) in primary clinical, neurocognitive and/or functional measures (Table 1), and 3) the absence of adverse effects of MEM that are significantly greater than PBO levels. The decision to not use traditional statistical significance as “Go” criteria for Aim 2 reflects this RFA’s call for “Pilot” studies, the need to identify candidate treatments for a subsequent larger “n” Confirmatory Efficacy R01 study, and the limits in sample size resulting from the 3-year R33 duration. Cohen defined a medium effect size ($d=0.5$) as one that is “visible to the naked eye,” and this amount of change is viewed as clinically meaningful in trials targeting negative symptoms.⁹⁹⁻¹⁰¹ This $d=0.5$ “Go” threshold for Aim 2 corresponds to a “number needed to treat” (NNT) value ≈ 3.62 . While a “Go” decision does not require identification of a biomarker predicting greater PACT sensitivity (Aim 3), the identification of one or more meaningful predictors that could be incorporated into a Confirmatory Efficacy trial would favorably impact a “Go” decision.

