Post-treatment protocol: On completion of 30 TCT sessions, participants will be offered the option of maintaining their assigned drug (PBO or MEM) through the 22-week durability assessments. Those who opt to discontinue the study drug will titrate off, over a 3-week period. After week 22, study blind will be broken, and subjects who continued to receive MEM will again be offered the option of titrating off of MEM vs. maintaining MEM treatment coordinated with, and under the supervision of, their primary provider.

Data Analysis: “Go/No Go” decisions are based on traditional statistical significance (Aim 1) and effect sizes (Aim 2). Formal statistical testing is conducted using linear mixed-effects (LME) models; hypothesis tests are 2-sided ($\alpha=.05$). Model parameters are estimated via the R lme4 package and Cohen’s d is estimated via the

EMAtools package. Type I errors are minimized by constraining the number of primary analyses; secondary analyses use false discovery rate corrections. Expected attrition rates are described above. Because outcome measures involve a “change from baseline”, baseline metrics are compared between PBO and MEM arms, and any baseline differences are addressed in the outcome analyses. Differential drop-out rates from PBO vs. MEM arms are monitored. Data are assumed to be missing at random; full information maximum likelihood estimators are used, and all data/cases are included in analyses. Clinical follow-up is pursued with all patients exiting the study through post-TCT week 12. Cohort differences: For between-subject contrasts (main effect of drug), differences in age, antipsychotic and anticholinergic loads are tested and used as covariates^{2,33,95}. Sex differences are tested for all measures. NIH Data Harmonization: 3 “PhenX Toolkit” (NOT-MH-15-009) measures of function are used; see above and “Resource Sharing Plan”.

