Subject “throughput”: We will enroll and screen 23 subjects/yr, test target engagement in 18 subjects/yr, and (conservatively) complete TCT training in 12 subjects/yr. This will yield 2 “target engagement” Aim 1 arms of n=27, and (conservatively) 2 TCT completion Aim 2 arms of n=18. Training capacity (2 TCT stations with morning and afternoon sessions on M, W and F, with T and Th “make-up” days for missed appointments, 48 weeks/year) allows for a “maximum throughput” of 19.2 subjects/yr. To reach the target of **12 TCT-completing subjects/year**, we would need to maintain training rates of **62.5% capacity**. This is well within our historical testing levels.

Power analyses: Consistent with the FOA, this study will adequately power tests of target engagement (Aim 1) for traditional significance, while the “Go” signal for therapeutic impact (Aim 2) is based on effect size ($d=0.5$). To detect target engagement for an LME model with $d=0.5$, 80% power, alpha=0.05, test-retest correlation=0.8, and a linear treatment effect, n=27 randomized participants are required per Hedeker et al (1999). This is a conservative estimate of d for target engagement, since empirically, d for target engagement with 20 mg MEM was 0.85 (Fig. 3). A future Confirmatory Efficacy trial will be powered to apply more robust approaches to Aim 2, e.g. Path Analysis⁶⁰ to study moderating effects of APS MEM sensitivity and biomarkers on both indirect (moderated-mediation) and direct paths between treatment and outcome.

Innovative ideas raise questions. Here are some answers:

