Differential drop-out rates from PBO vs. MEM arms are monitored. Clinical follow-up is pursued with all patients exiting the study through post-TCT week 12.

Cohort differences: For between-subject contrasts (drug), baseline demographic, clinical, antipsychotic/anticholinergic load and performance differences are tested and used as covariates if indicated. Sex differences are tested for all measures.

Procedures for Alternative or Unexpected Results: Linear mixed-effects models allow for the analysis of all available data using an intent-to-treat approach. This approach, however, assumes that data are missing at random. A potential concern is nonrandom dropout, particularly when dropout is related to the (missing) outcomes; that is, not missing at random. To make the missing at random assumption more plausible, we will explore the use of auxiliary variables. Auxiliary variables are covariates that predict both dropout and outcomes. By adding

auxiliary variables to our models, nonrandom dropout is corrected by conditioning treatment effects on the predictors of dropout.

Primary Efficacy Endpoint(s): Aim 1: Target engagement – APS learning will be significantly greater under MEM vs. PBO conditions. Aim 2: Pilot trial - Compared to PBO arm patients, MEM arm patients will exhibit greater clinical benefit, as indicated by one or more of the following: greater, faster or more durable improvements in PANSSt (reduced scores; see below, "Go/No-Go"), MCCBc (increased scores) or WHODAS (reduced scores).

Secondary Efficacy Endpoint(s): Aim 3: Biomarkers - baseline levels of specific neurocognitive or EEG-based measures, or changes in specific measures with initial MEM exposure, predict greater sensitivity to MEM-enhanced neurocognitive, clinical or functional gains over 30 sessions of TCT.

Analyses testing primary and secondary hypotheses will include all subjects' clinical, neurocognitive and functional assessments. Data from subjects who do not complete the full study are carried forward in an "intent to treat" design, and their data are analyzed using linear mixed models. Separate analyses will compare completion / drop-out rates across arms, as well as a 14-item 7-point Likert scale assessing treatment satisfaction.

Go/No-Go decision and primary and secondary endpoints

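### The Aim 1 Go gate names its deciding contrast in one place only; elsewhere the wording also admits an unadjusted Test 2 comparison with about half the power

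*Combined protocol and SAP*

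**What the plan says.** The gate appears in several places.

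- Outcome and Go Decisions requires "confirmation of target engagement (APS learning, MEM>PBO, p<0.05". Table 1, item 1 says the same. Neither names a contrast.
- Section 4.4, Primary Efficacy Endpoint(s), says "APS learning will be significantly greater under MEM vs. PBO conditions". Again no contrast is named.
- Specific Procedures says "MEM effects on APS learning are assessed both within-subject (APS (Test 1 - Test 2) for MEM group subjects", and describes that change as a key measure of sensitivity to memantine. It adds "between subjects (APS Test 2, PBO vs. MEM groups". Neither comparison carries a p threshold or a Go label, and neither is called supportive.
- Data Analysis, Aim 1 says "A significant interaction between contrast coded drug (PBO vs. MEM) and Test (Test 1 vs. Test 2) predictors on APS learning is a “Go” criteria"; it adds that this result would confirm target engagement. The sentence before it leaves the model open: "As appropriate, effect sizes and inferential statistics are based on standard regression or LME models with random intercepts".

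The Power analyses paragraph gives, for d=0.5, "80% power, alpha=0.05, test-retest correlation=0.8, and a linear treatment effect, n=27 randomized participants are required". Section 4.4 repeats this as a per-group figure. Tests are two-sided at 5%.

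**The concern.** The Test 2 comparison between arms and the drug x Test interaction are different tests. The first ignores Test 1. The second subtracts it. Their relative power depends on the correlation between the two tests, and they can fall on opposite sides of p=0.05 in the same 54 patients.

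An analyst working from Table 1 or section 4.4 sees only MEM above PBO. That analyst could reasonably run the Test 2 comparison listed in Specific Procedures, especially as Data Analysis, Aim 1 remarks that the arms are matched on Test 1 by the stratified assignment. An analyst working from the interaction sentence would run another test. If the deciding contrast is not fixed in every place, the Go verdict can depend on which section was followed.

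**Working it through.** **Inputs.** d=0.5, r=0.8, two-sided alpha 0.05, 80% power, 27 per arm (Power analyses; section 4.4). Assumptions: d is in units of the single-test SD (set to 1), variances are equal, scores are normal, all 54 patients have complete data, and stratification is ignored.

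**Step 1: reproduce n=27.** With two tests, the drug x Test interaction is a two-sample comparison of the change score.

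- SD of change = sqrt(2(1-0.8)) = 0.632.
- n per arm = 2 x (1.960+0.842)^2 x 0.40 / 0.25 = 25.1, so 26 by the normal formula. The noncentral t gives exactly 27.

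**Step 2: try the other contrasts.**

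- Test 2 only (SD 1): 2 x 7.851 x 1 / 0.25 = 62.8, so 63 (normal) or 64 (t).
- Test 2 adjusted for Test 1 (variance 1-0.8^2 = 0.36): 2 x 7.851 x 0.36 / 0.25 = 22.6, so 23 (normal) or 24 (t).
- A one-sided interaction test needs 20.

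Of the variants tried, only the two-sided interaction gives 27.

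**Step 3: power at 27 per arm, d=0.5.** The noncentrality is 0.5 / (SD x sqrt(2/27)), with sqrt(2/27) = 0.272. At r=0.8 it is 1.84 for Test 2 only, 2.90 for the interaction and 3.06 for the adjusted test.

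| r | Test 2 only | Interaction | Test 2 adjusted for Test 1 |
|---|---|---|---|
| 0.2 | 43.8% | 29.7% | 45% |
| 0.3 | 43.8% | 33.1% | 47% |
| 0.5 | 43.8% | 43.8% | 55% |
| 0.8 | 43.8% | 81.3% | 85% |

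Simulation, which also counts the cost of chance imbalance at Test 1, puts the adjusted test at 54% for r=0.5. The documents support only r=0.8; the lower values are an assumed range.

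**Step 4: disagreement.** In simulation (40,000 trials per setting, true d=0.5, significance counted in favour of MEM), the Test 2 and interaction verdicts differ in 29% of trials at r=0.2 and about 47% at r=0.8. At r=0.8 at least one is significant in 86.1%, Test 2 in 43.6% and the interaction in 81.0%. So the interaction alone passes in 86.1 - 43.6 = 42.5% and Test 2 alone in 86.1 - 81.0 = 5.1%.

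**Step 5: error if either were accepted.** With no drug effect, at least one of the two favours MEM significantly in about 4.3% to 4.7% of trials, against 2.5% for one test. This applies only under an either-counts rule.

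**The case against.** The strongest reply is that the gate is already specified. Data Analysis, Aim 1 names the interaction, no other contrast has both a p threshold and a Go label, and the sample size fits the interaction. Section 4.4 refers to the Research Strategy for details and specifies mixed models for formal testing. The choice between regression and a mixed model is one of model rather than contrast: with two complete tests, regressing the change score and fitting the interaction test the same thing. If APS learning means the Test 1 to Test 2 reduction, as that paragraph defines it, MEM above PBO on learning already is the interaction on APS.

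Most of this stands. It makes the interaction the best reading. It does not make it the only one. The same paragraph's definition gives one learning value per patient, so a Test interaction on learning cannot be fitted as written. Measuring Target Engagement and section 4.3 define learning within a session, and under that definition the Test 2 comparison is a natural reading of MEM above PBO. Nothing calls that comparison supportive.

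A reader might go further and infer that a significant Test 1 to Test 2 change in the MEM arm could by itself confirm engagement, so that practice effects could trigger a Go. The documents do not support this. That change is labelled a sensitivity measure, within-subject engagement is used as a predictor in secondary analyses, and a one-arm change cannot show MEM above PBO. Nor does any passage say that a positive result on either between-arm contrast is enough, so the figures in step 5 are conditional and do not describe the plan's error rate.

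**Conclusion.** The point holds as a specification gap with a better analysis available. The plan names its gate once, powers that contrast correctly, and does not carry it through to the Go rule, Table 1, Specific Procedures or section 4.4. The competing Test 2 reading has 43.8% power against 81.3%, and the two readings give opposite verdicts in 29% to about 47% of trials at d=0.5.

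Separately, the interaction is not the most efficient use of data already in hand. Adjusting for Test 1 learning, which is measured before randomisation and already used for stratification, gains about 4 percentage points of power at r=0.8 (85% against 81%) and about 11 at r=0.5 (55% against 44%). It does at least as well as either alternative at every r examined.

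These figures rest on the assumptions listed in the working. They also take r as the correlation of the analysed score. If that score is the within-session difference, the stated 0.8 must hold for the difference itself; interaction power falls to 64% at r=0.7 and 52% at r=0.6.

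**What to change.** Make one contrast decide the Aim 1 Go: the MEM-PBO difference in Test 2 APS learning, adjusted for pre-randomisation Test 1 APS learning, two-sided alpha 0.05, direction MEM above PBO. Use identical wording in Outcome and Go Decisions, Table 1 item 1, Specific Procedures, Data Analysis Aim 1, and the section 4.4 endpoint. Use one definition of APS learning throughout, so that each patient has a separate Test 1 and Test 2 value.

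State that the unadjusted Test 2 comparison and the drug x Test interaction are supportive with no role in the Go, and that the within-MEM-arm change is descriptive and serves only as the sensitivity measure. Restate the power for the adjusted test.

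If the sponsor prefers the interaction, name it alone in all these places and attach the 80% power statement to it.

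The cost is wording only: no new data, visits or patients. The sponsor gives up the option of claiming target engagement from an alternative contrast.
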